5.2.5 Approaches and Analyses for Missing Data and Other Data Issues

[figure not shown]
Missing data will not be imputed and will be considered missing for data analysis, resulting in a possible reduced sample size.

6 Summary of General Study Data

6.1 Subject Disposition

Participants will be provided the PISCF and once informed, written consent is provided they will be enrolled into the study. Participants will then be screened to ensure they meet the inclusion criteria and do not meet any of the exclusion criteria. Subsequently, participants who are identified as suitable for the study will be provided a unique participant code. The number of participants enrolled and those that failed screening will be recorded. For those that participate in the study, the stage that they reach will also be recorded (e.g., interventional visit 2, as depicted in Figure 6.1.1). For those that participate in the study and drop out, individual responses will be asked to be provided and recorded. Population membership (ITT, PP, etc.) is provided in section 4.1.

Figure 6.1.1: Skeleton flow diagram depicting participant disposition

6.2 Protocol Deviations

Specific protocol deviations are listed below and categorized as either a major deviation (i.e., data to be excluded) or minor (i.e., data to be included).

6.2.1 Major deviations

- **Failure to attend:** If a participant fails to attend two subsequent visits (e.g. interventional visits 2 & 3), the individual data collected from the participant will be excluded.
- **Suspicion of tampering:** If it is suspected that the participant has tampered with their PIVCs, as evidenced by breakage of the anti-tampering device, leakage from the extension, perforated dressing the data collected from the participant will be excluded.
- **Insertion of alternate gauge PIVCs:** Data will be excluded from participants where, in the unanticipated circumstance, a 20G PIVC has been inserted into one arm (e.g., left) of the participant and a 22G PIVC has been inserted into the other arm (e.g., right). Participants will be asked to re-enroll and re-consent after a period of 2 weeks.
- **Insertion of identical length PIVCs:** Data will be excluded from participants where, in the unanticipated circumstance, two PIVCs of the same length are inserted into the participant regardless of the gauge. Participants will be asked to re-enroll and re-consent after a period of 2 weeks.
- **Contraction of a common cold/respiratory infection:** If a participant contracts a common cold/respiratory infection during their interventional visit, the individual data collected from that participant will be excluded and they will be removed from the study.

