8 PARTICIPANT DISCONTINUATION/WITHDRAWAL

8.1 Discontinuation/Withdrawal

- A participant may withdraw from the study at any time at his/her own request or may be withdrawn at any time at the discretion of the investigator or sponsor for safety, behavioral, compliance, or administrative reasons. This is expected to be uncommon.
- At the time of discontinuing from the study, any indwelling catheters will be safely removed and disposed of in accordance with the Instructions For Use as per standard protocol without any data collected. Additionally, the sites of insertion will be assessed for signs of infection and extravasation. The participant will be followed-up within 96 hours for participant safety and to ensure no adverse events have occurred following removal of indwelling catheters.
- If the participant withdraws consent for disclosure of future information, the sponsor may retain and continue to use any data collected before such a withdrawal of consent.
- If a participant withdraws from the study, he/she may request destruction of any samples taken and not tested, and the investigator must document this in the site study records.

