8.3 Patient replacement

Any participants lost to the current study (withdrawn or lost to follow-up) will be replaced through normal screening processes and allocated to the incomplete experimental group to ensure at least 20 participant completers for each catheter gauge. Replacement participants will be started in the same order as drop-out/withdrawal; drop-outs will not be considered eligible for readmission due to potential effects of prior catheter placement on subsequent study outcomes.

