10.4 General Considerations

Participants who have withdrawn consent for continuation of the study (i.e., dropouts or non-compliant) will be included in the analysis by modern imputation methods for missing data. In the unforeseen circumstance of a protocol violation (e.g., 20G PIVC instead of 22G PIVC; blood was collected into 6mL vacutainer before 2mL for a specific participant), the data will be analyzed ‘as treated’ – that is, data will be analyzed as the participant’s actual received intervention. However, in the unforeseen circumstance of a protocol violation whereby a participant receives the wrong intervention (e.g., two different gauge catheters; two 20G catheters of the same length), they will be treated as per protocol and thus their data will be excluded from the study.

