10.5 Primary Endpoint(s)

Comparisons across and between device configurations (i.e., length/gauge) will be made using logrank tests for indwell time. The primary endpoint will be evaluated using statistical modeling software (Prism, Release 8.3; GraphPad Software Inc., USA) or R (R 3.6.2 or higher).

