4.1 Population Definitions

In the unforeseen circumstance of a protocol deviation (e.g., 20G PIVC instead of 22G PIVC; blood was collected into 6mL vacutainer before 2mL for a specific participant), the data will be analyzed “as treated” - that is, data will be analyzed as the participant’s actual received intervention. However, in the unforeseen circumstance of a protocol deviation whereby a participant receives the wrong intervention (e.g., two different gauge catheters; two 20G catheters of the same length), they will be treated as per protocol (PP) and thus their data will be excluded from the study because paired comparison of catheter length will not be possible.

5 Statistical Analysis/Calculations

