5.2.1 Statistical Analysis of Primary Endpoint

5.2.1.1 Indwell Time

It is hypothesized that:

- PIVC indwell time will be greater for longer catheters
- PIVC indwell time will be greater for catheters of smaller gauge (larger bore)

In order to test these hypotheses, catheter indwell time will be assessed using survival analysis, including:

- Kaplan-Meier survival curves including Log-Rank test p-value
- Cox Proportional Hazards Model with Hazard Ratios for each device vs. default device condition (BD Nexiva 20G x 1 inch) and associated 95% Confidence Intervals. Effect of the following covariates will be investigated: gender, age, BMI and dominant arm.

Main analysis will be performed stratified by device, depending on the results pooled analyses by gauge or by catheter length might be performed. An example of the Kaplan-Meier curve and associated metrics is provided in Appendix B by Figure B.1.1. An example of the Hazard Ratios extracted from the Cox Proportional Hazards models is provided in Appendix A by Table A.4.2.

For the purpose of this survival analysis, device failure (inability to flush or draw blood, see section 6.6) will be identified as follows:

- Blood Draw: Variables DEBLDCS equal to “N” and DEBLDRS equal to “N” from table INBCINBC
- Flush: Variables DEFLSSU equal to “N” and DEFLSRS equal to “N” from table INFL

Failure can occur during any of the 7 repeats of the blood draw (for either tube volumes) or flush processes, as highlighted in orange on Table 2.7.1, for right or left arm, per randomization schedule. Date-time of failure is then given by the aggregation of variables DEDTN & DEFTM, from tables INBCINBC or INFL, respectively for blood draw or flush.

Additional Indwell Time summary statistics and graphical representation will be provided as represented in Appendix A by Table A.4.1 and in Appendix B by Figure B.2.1, respectively.

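### SAP 6.2.1 invites wrongly cannulated participants back after two weeks, although the protocol's reason for refusing readmission of drop-outs applies equally to them

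*SAP*

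**What the plan says.** SAP 6.2.1 lists two insertion errors as major deviations: a 20G catheter in one arm with a 22G in the other, and two catheters of equal length. In both cases the data are excluded, and both entries end with the same sentence: "Participants will be asked to re-enroll and re-consent after a period of 2 weeks".

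Three other passages bear on this:

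- Protocol 8.3 covers replacement: "Any participants lost to the current study (withdrawn or lost to follow-up) will be replaced through normal screening processes". It then closes the way back: "drop-outs will not be considered eligible for readmission due to potential effects of prior catheter placement on subsequent study outcomes".
- Protocol 10.4 covers wrong insertions directly. It says of these participants that "they will be treated as per protocol and thus their data will be excluded from the study", and offers no return.
- SAP 4.1 also only excludes, giving as its reason the loss of pairing: "thus their data will be excluded from the study because paired comparison of catheter length will not be possible".

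The re-enrolment route therefore exists only in SAP 6.2.1.

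**The concern.** A participant with a wrong insertion has had catheters placed in the lower-arm cephalic veins of both arms. Re-enrolment sends a second set to the same target veins. That is the exposure protocol 8.3 gives as its reason for refusing drop-outs.

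The documents treat the mechanism as plausible. Protocol 2.3.1 lists thrombosis and thrombophlebitis among the cannulation risks. Intravenous thrombus is a secondary endpoint, and SAP 5.2.2.3 makes it a candidate predictor of indwell time. Residual change in the vein could shorten the patency of the second set or raise thrombus counts.

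The primary analysis has nothing that would reveal this. Protocol 10.5 states: "Comparisons across and between device configurations (i.e., length/gauge) will be made using logrank tests for indwell time". For the Cox model, SAP 5.2.1.1 states: "Effect of the following covariates will be investigated: gender, age, BMI and dominant arm". There is no term for earlier cannulation and no sensitivity analysis without re-enrolled participants.

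**Working it through.** **1. Does the protocol's bar reach these participants?** By its wording, 8.3 speaks of drop-outs, in a paragraph about people withdrawn or lost to follow-up. Someone excluded for a staff error is covered only if counted as withdrawn. Protocol 8.1 would permit that, since a participant "may be withdrawn at any time at the discretion of the investigator or sponsor for safety, behavioral, compliance, or administrative reasons", but it does not say that wrong insertion is such a case. By its reason, 8.3 depends on earlier catheter placement and not on why the person left, so the reason applies in full.

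**2. Is the interval supported?** No passage explains the two weeks or requires earlier vein changes to have resolved. The last scheduled visit (V6, protocol 4.1) is 24 to 96 hours after removal.

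**3. Which comparisons are exposed?**

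- *Length* is compared between the two arms of one person (protocol 4.2). Both arms were cannulated before, so a shared effect largely cancels.
- It need not cancel if the earlier devices differed between arms. After a mixed-gauge error the gauges differ by definition, and the lengths may differ too. After an equal-length error the earlier length was the same in both arms, so it cannot produce a difference between arms.
- *Gauge* is compared between participants, so carry-over does not cancel there. The same holds for thrombus occurrence compared between gauges.

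**4. The plan's own power figure.** Inputs from SAP 2.4: 19 and 20 catheters, medians 1 and 3 days, hazard ratio 0.3333, 3 days of follow-up, no loss, two-sided alpha 0.05.

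- Expected events under exponential survival: 19 × (1 − 0.5³) + 20 × (1 − 0.5) = 16.625 + 10 = 26.625.
- Schoenfeld: √(26.625 × 19/39 × 20/39) × ln 3 − 1.96 = 2.83 − 1.96 = 0.87, which gives power 0.809.
- A Lakatos-type log-rank calculation gives 0.806. The stated 0.8054 is reproduced.

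This figure does not bear on re-enrolment, but it supplies the base case for the next step.

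**5. Size of the effect, on assumed values.** The documents give neither a deviation rate nor a carry-over size. One re-enrolled person is 1/20 = 5% of a gauge group; two are 10%. The illustration assumes:

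- 20 against 20 independent catheters, with the medians above;
- failure hazard multiplied by 1.5 or 2 in re-enrolled participants;
- for length, equal carry-over in both arms;
- for gauge, all re-enrolled participants in one group (under the alternative, the longer-surviving one);
- 3,000 simulations per case.

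| Re-enrolled, hazard factor | Length: type I error | Length: power | Gauge: type I error | Gauge: power |
|---|---|---|---|---|
| None | 0.055 | 0.818 | 0.055 | 0.822 |
| 1, ×1.5 | 0.056 | 0.824 | 0.058 | 0.799 |
| 1, ×2 | 0.061 | 0.807 | 0.051 | 0.799 |
| 2, ×1.5 | 0.053 | 0.820 | 0.052 | 0.796 |
| 2, ×2 | 0.050 | 0.817 | 0.064 | 0.760 |

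Simulation standard errors are about √(0.055 × 0.945/3000) = 0.004 for type I error and √(0.82 × 0.18/3000) = 0.007 for power. The length results do not move beyond noise. Gauge power falls by about 2 to 6 points. Carry-over that differs between arms was not simulated.

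**The case against.** The strongest reply is that there is no contradiction in the text. Protocol 8.3 concerns people who left, and SAP 6.2.1 concerns people who received the wrong device. That stands as a reading of the words. It does not answer the reason that 8.3 gives.

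A second reply is that re-enrolled participants go through screening again (SAP 6.1). They would have cephalic ultrasound at screening and before insertion, a minimum vein diameter, and an exclusion for conditions that could confound the results. Gross thrombus or vein change would probably be seen. This lowers the risk, but no criterion mentions residual thrombus or recent cannulation. SAP 2.2 also lets a medical monitor admit people who miss a criterion, on safety grounds alone.

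Third, the event is described as unanticipated, participants may decline to return, and this is a feasibility study without acceptance criteria (SAP 2.9). All of that is true, and it keeps the point minor.

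A reader might infer that carry-over *will* bias the primary length comparison, because it depends on which length was in which arm the first time. The documents do not support that. Protocol 8.3 speaks only of potential effects, and the mechanism cannot operate after an equal-length error. After a mixed-gauge error, a fresh random allocation would not align the earlier asymmetry with length in any systematic way. The documents do not say whether a re-enrolled participant is randomized again.

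**Conclusion.** The point holds as an inconsistency of rationale with a possible analytic consequence. The SAP adds an enrolment route that the protocol does not contain, for people to whom the protocol's stated reason against readmission applies, with an unexplained interval and no safeguard in the primary analysis.

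Carry-over could enter if the deviation happens. The gauge comparison and the thrombus endpoints are the most exposed. The paired length comparison is largely protected unless the earlier devices differed between arms.

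The true size cannot be derived from the documents. On the assumed values, one or two re-enrolled participants cost at most about 6 points of gauge power (0.82 to 0.76) and leave the length comparison essentially unchanged. That rests on the assumed hazard factors, independence between catheters, and equal carry-over in both arms for length.

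**What to change.** Reconcile the two passages so that no participant contributes a second set of catheters to the analysis:

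- Delete both re-enrolment sentences in SAP 6.2.1 and state that participants excluded for wrong insertion are replaced by newly screened volunteers.
- Extend protocol 8.3 to name these participants. As worded, it replaces only those withdrawn or lost, so the SAP deletion alone could leave a gauge group short.

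If re-enrolment is kept, put it in the protocol with a justification for the interval, and report the primary analysis with and without re-enrolled participants.

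The cost is a few sentences in two documents, and one or two extra screenings if the error occurs; protocol section 5 cites a registry of more than 700 volunteers. Replacement keeps 20 per gauge, and power for length within a gauge stays at 0.813 (20 against 20, Lakatos-type calculation). Exclusion without replacement would give 0.793, 0.771 or 0.748 with one, two or three pairs lost.

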10.3 Analysis Population

The following populations are defined as:

Population	Description
Enrolled	All participants who sign the ICF
Evaluable	All participants who complete the study until either the catheter fails or the protocol is completed (i.e., 72 hours)

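### SAP 6.2.1 deletes all data from participants who miss two visits, are suspected of tampering or catch a cold, where a written censoring rule would keep the patency and failures already observed

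*SAP*

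**What the plan says.** SAP 6.2 divides protocol deviations into major, for which data are excluded, and minor, for which they are kept. SAP 6.2.1 lists among the major ones three events that can only happen after randomisation:

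- Missed visits: "If a participant fails to attend two subsequent visits (e.g. interventional visits 2 & 3), the individual data collected from the participant will be excluded".
- Suspected tampering, "as evidenced by breakage of the anti-tampering device, leakage from the extension, perforated dressing the data collected from the participant will be excluded".
- Respiratory infection: "If a participant contracts a common cold/respiratory infection during their interventional visit, the individual data collected from that participant will be excluded". The participant is also removed from the study.

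None of the three is limited to data collected after the event.

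The primary endpoint (SAP 2.8.1) is time from insertion to failure. SAP 5.2.1.1 analyses it by Kaplan-Meier curves with a log-rank test and by a Cox model. Neither section, nor SAP 5.2.5, says when a catheter is censored. SAP 5.2.5 says: "Missing data will not be imputed and will be considered missing for data analysis". Protocol 10.4 says that participants who withdraw, described there as dropouts or non-compliant, "will be included in the analysis by modern imputation methods for missing data". Protocol 10.3 defines an evaluable set as "All participants who complete the study until either the catheter fails or the protocol is completed", without assigning it to any analysis. Protocol 8.3 replaces withdrawn or lost participants so that each gauge reaches at least 20 completers.

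**The concern.** A participant who develops a cold on Day 3 has had both lengths in place and regularly tested until then. SAP 4.1 justifies excluding wrongly treated participants because the paired length comparison is lost. That reason does not apply here, since the pair is intact up to the event. A cold may confound haemolysis measured after onset (protocol 2.1 names inflammatory status as a factor), but not measurements from before onset.

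Three things are at stake: observed patency time, failures already on record, and selection. Selection arises because a participant whose catheters last longer is exposed to these triggers for longer, and because some signs used as evidence of tampering can accompany a catheter problem. Separately, two analysts following protocol 10.4 and SAP 6.2.1 would analyse different participants for the primary endpoint.

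**Working it through.** **1. The plan's own figure.** Inputs from SAP 2.4: medians of 1 and 3 days, hazard ratio 0.3333, 3 days of follow-up, 19 and 20 catheters, two-sided 0.05, zero loss, stated power 0.8054. With exponential survival:

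- Failure by day 3: 1 - exp(-3 ln2/1) = 0.875 (short) and 1 - exp(-3 ln2/3) = 0.500 (long).
- Expected events: D = 19 x 0.875 + 20 x 0.500 = 26.625.
- Schoenfeld: power = Phi(sqrt(D a(1-a)) x ln 3 - 1.96) with a = 19/39, which is Phi(2.833 - 1.960) = 0.809.
- A Lakatos-type log-rank calculation gives 0.806. The Freedman form gives 0.732 and does not match.

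The stated power reproduces, and it assumes that nobody is lost. It also treats the two lengths as independent groups; the figures in step 3 inherit that.

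**2. What one deletion removes.** Under SAP Table 2.7.1, a cold reported at the Day 3 morning visit (T+48 h), with both catheters working, deletes 2 x 48 = 96 catheter-hours. It also deletes 4 draws x 2 tubes x 2 catheters = 16 cfHb samples.

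**3. Power without replacement.** With k of 20 participants in a gauge group deleted, D = (20 - k) x 1.375.

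| k | D | Lakatos | Schoenfeld |
|---|---|---|---|
| 0 | 27.5 | 0.813 | 0.821 |
| 1 | 26.1 | 0.793 | 0.802 |
| 2 | 24.8 | 0.771 | 0.780 |
| 3 | 23.4 | 0.748 | 0.757 |

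**4. Deletion unrelated to failure.** A simulation of 400,000 participants used the SAP medians. Its assumptions are exponential survival, independent catheters, failures known when they occur, and a constant hazard of an excluding event that acts while either catheter is in place. The three-day risk is assumed at 5%, 10% and 20%.

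| | 5% | 10% | 20% |
|---|---|---|---|
| Participants deleted | 4.1% | 8.2% | 16.3% |
| Same, per 20 | 0.8 | 1.6 | 3.3 |
| Deleted with a 1-inch failure already recorded | 47.0% | 46.5% | 46.3% |
| Deleted with a 1.75-inch failure already recorded | 10.3% | 10.7% | 10.1% |
| Observed days lost per deletion, 1 inch + 1.75 inch | 0.84 + 1.26 | 0.84 + 1.24 | 0.82 + 1.21 |
| 72-h survival, 1.75 inch, after deletion (true 0.500) | 0.495 | 0.490 | 0.478 |
| 72-h survival, 1 inch, after deletion (true 0.125) | 0.123 | 0.121 | 0.119 |
| Failure rate per day, 1.75 inch, after deletion (true 0.231) | 0.235 | 0.238 | 0.247 |
| Failure rate per day, 1 inch, after deletion (true 0.693) | 0.698 | 0.703 | 0.712 |

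At 10%, deletion takes 10.0% of surviving 1.75-inch catheters and 6.3% of failed ones. By hand: 0.5 x 0.900 / (0.5 x 0.900 + 0.5 x 0.937) = 0.490, as simulated. Censoring at the event and keeping earlier failures returns 0.231 per day for the 1.75-inch catheter and 0.695 for the 1-inch.

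Both lengths shift the same way, so their ratio barely moves: 0.235/0.698 = 0.337, 0.238/0.703 = 0.339 and 0.247/0.712 = 0.347, against 0.333.

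**5. Deletion linked to failure.** If every deleted participant in a gauge group had a failed 1.75-inch catheter, its 72-hour failure would go from 10/20 = 50% to 9/19 = 47.4% (one deleted) or 8/18 = 44.4% (two). This runs in the opposite direction to step 4, and no document gives a rate for it.

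**The case against.** Much of the case on the other side stands, and it rules out several stronger readings.

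- *A reader might infer that the plan never censors.* The mock indwell listing (SAP Table C.0.5) carries status 0 before 72 h, for example at 28.76, 37.93 and 61.41 h. The rows are dummies, but the data structure allows early censoring. What is missing is a written rule, and SAP 6.2.1 takes these three cases out before any such rule could apply.
- *A reader might infer that leakage alone deletes a participant and so lengthens apparent indwell time.* The condition is suspected tampering; leakage and a perforated dressing are listed as evidence for it. Leakage is not itself failure under SAP 6.6. An overlap remains: protocol 2.3.1 attributes leakage to loose components, and the mock failure-mode table lists an insecure Luer connection. The figures in step 5 are a chosen scenario.
- *A reader might infer that the randomised length comparison is broken.* Both catheters leave together, so the lengths stay balanced in number. Gauge is compared between participants and lacks that protection.
- *A reader might infer a conflict among four sections.* SAP 5.2.5 and 6.2.1 are compatible, and the evaluable set in protocol 10.3 is tied to no analysis. The clear contradiction is protocol 10.4 against the SAP.
- *A reader might infer that censoring needs no assumptions.* It assumes a non-informative trigger, and a missed visit or tampering may be related to failure.

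Replacement under protocol 8.3 may also prevent the power loss in step 3. Finally, this is a feasibility study with no acceptance criteria.

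**Conclusion.** The point holds as an improvement to the analysis rule. Followed as written, SAP 6.2.1 discards valid patency time and recorded failures that the chosen survival methods can use, and it contradicts protocol 10.4. At the planning medians, close to half of deleted participants would already have a recorded 1-inch failure. Each deletion loses about 2.0 to 2.1 catheter-days.

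Bias from triggers unrelated to failure is small: at most 0.022 in 72-hour survival of the 1.75-inch catheter at an assumed 20% risk, and towards shorter indwell. Triggers linked to failure would push the other way by an amount the documents do not allow anyone to estimate. Without replacement, one to three deletions in a gauge group cost about 0.02 to 0.07 of power. With replacement the numbers return, but the discarded events and the selection remain.

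These figures rest on the assumed exclusion rates, exponential survival and independent catheters.

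**What to change.** For these three triggers only:

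1. Include all randomised participants in whom the assigned pair was inserted.
2. Keep as an event any catheter that met the existing failure definition (SAP 6.6) before the trigger.
3. Censor a catheter still working at its last successful flush or draw before the trigger.
4. Keep repeated measures up to the trigger in the mixed models.
5. Pre-specify how a catheter that fails at the same time as suspected tampering is coded, with the alternative coding as a sensitivity analysis.
6. Run the SAP 6.2.1 exclusions as a further sensitivity analysis.
7. Reconcile protocol 10.3 and 10.4 with SAP 5.2.5 and 6.2.1, so that one rule covers dropouts and non-compliant participants.

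Whether a participant is removed from the study is a matter of conduct and stays as it is. The cost is wording in both documents, a little more analysis work, and reliance on non-informative censoring, which items 5 and 6 probe.
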